**Abstract:**

Background: High-resolution, relational, resonance-based, electroencephalic mirroring (HIRREM®) is a closed-loop, allostatic, acoustic stimulation neurotechnology that uses software-guided algorithmic analysis to identify and translate selected brain frequencies into audible tones to support real-time self-optimization of brain activity. Prior research demonstrates that the use of HIRREM is associated with reduced symptoms of insomnia, and traumatic stress and anxiety, and improved autonomic cardiovascular regulation across heterogeneous cohorts. HIRREM has been safe and well tolerated in about 500 people across six IRB-approved studies. However, the current in-office HIRREM approach remains very operator dependent (extensive Technologist education and experience) and takes a sizeable time commitment from the participant (typically ten to twenty sessions of 90-120 minutes each). To reduce participant time required, and operator dependence, while increasing scalability, a new generation of hardware and software has been developed. Based on the same core technology and algorithms to mirror brainwaves with audible tones, this now includes the use of faster, 64-bit processing architecture for faster feedback, the use of 4 sensors, and the use of a standard series of protocols, all done with eyes closed (HIRREM Standard Operating Procedure, HIRREM-SOP). Although only 2 sensors are active at a time, applying 4 sensors, for which the software can switch from one pair to the other automatically, cuts in half the number of sensor placement changes needed, with reduced session time and interruptions. The placebo condition has also been modified so there is randomness to both the pitch and the timing of the tones, using tones that have not been acoustically engineered. This pilot study will evaluate feasibility and effects of this standardized, fixed dose, enhanced approach, and the effectiveness of blinding for the placebo condition in participants with symptoms of insomnia.

**Objectives:**

The primary objective of this randomized pilot study is to evaluate the effect of 10 sessions of standardized acoustic stimulation linked to brain activity (HIRREM-SOP), compared to 10 sessions of nonspecific acoustic stimulation not linked to brain activity (randomly generated tones), on symptoms of insomnia, based on change in ISI score from V1 to V3. The secondary objective is to evaluate the effectiveness of blinding for the placebo condition based on the expectation measure regarding group assignment prior to the 5th session. Tertiary, exploratory objectives include evaluation of the effects on other symptom and physiological measures.

**Methods:**

This will be a randomized, single site, double-blinded, placebo-controlled, pilot clinical trial, enrolling adults aged 18 or older, who have self-reported symptoms of at least mild insomnia. Up to 24 will be enrolled, seeking 20 to complete the protocol. Participants will be randomly assigned to receive 10 sessions of either acoustic stimulation linked to brainwave activity (HIRREM-SOP, BCC), or nonspecific acoustic stimulation with randomly generated tones not linked to brain activity (nonspecific acoustic stimulation, NCC), using otherwise identical study procedures, over a maximum of 4 weeks. Both groups will continue their other current care throughout. There will be pre- and post-intervention data collection to include physiological outcomes (BP, HR, and measures of autonomic cardiovascular

regulation), as well as symptom inventories for insomnia (Insomnia Severity Index, ISI; Pittsburgh Sleep Quality Index, PSQI; and the Epworth Sleepiness Score, ESS), depression (Center for Epidemiological Studies- Depression Scale, CES-D), anxiety (Generalized Anxiety Disorder-7, GAD-7), and stress (Perceived Stress Scale, PSS). Measures will be collected at an enrollment visit (V1), and the intervention will begin 0-14 days thereafter. Post-intervention data collections will be obtained at 0-14 days (V2) after completion of the intervention, and 4-6 weeks (V3, primary outcome) after the V2. An expectation measure for group assignment will be obtained at V1, prior to the 5th intervention session, and at V3 data collections. The primary outcome is differential change in ISI from V1 to V3. The secondary outcome is the effectiveness of blinding for the placebo condition based on the expectation measure regarding group assignment prior to the 5th session. All other measures are tertiary and exploratory. Following V3, those in the NCC group will be offered the opportunity to cross over to receive a course of acoustic stimulation linked to brainwaves, and will continue to be followed for data collections at 0-14 days (V4) after completing their crossover sessions, and 4-6 weeks (V5) after V4. Linear mixed models (LMMs) will be used to contrast longitudinal changes in systolic and diastolic blood pressure between the BCC and NCC groups. Mean contrasts will be used to compare the changes in ISI between groups from V1 to V3, our primary test of efficacy. Comparisons of changes in all other outcomes will be assessed in a similar fashion.

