There will be pre- and post-intervention data collection to include physiological outcomes (BP, HR, and measures of autonomic cardiovascular regulation), as well as symptom inventories for insomnia (Insomnia Severity Index, ISI, Pittsburgh Sleep Quality Index (PSQI), and the Epworth Sleepiness Score (ESS), depression (Center for Epidemiological Studies- Depression Scale, CES-D), anxiety (Generalized Anxiety Disorder-7, GAD-7), and stress (Perceived Stress Scale, PSS).

Measures will be collected at an enrollment visit (V1), and the intervention will begin 0-14 days thereafter. Post-intervention data collections will be obtained at 0-14 days (V2) following completion of the intervention, and 4-6 weeks (V3, primary outcome) following V2. Analyses for primary outcomes will include differential change in ISI from V1 to V3, and the expectation measure for group assignment prior to the 5th session. The blind will be broken at the V3 visit, and those in the NCC group will be offered the opportunity to cross over to receive acoustic stimulation linked to brainwaves. All study personnel except for the Technologists will remain blinded to group assignment, so that data collection will be carried out by individuals without knowledge of group assignment.

Sample Size and Statistical Analysis:

As a pilot study evaluating upgraded technology, and a standardized protocol, there are no data on which to base formal sample size estimates. The protocol is thus written with the goal of having 20 subjects (10 per group) to be enrolled and complete the study. For analysis, we will utilize linear mixed models (LMMs) to contrast longitudinal changes in ISI scores between the BCC and NCC groups. Mean contrasts will be used to compare the changes in ISI between groups from V1 to V3, our primary test of efficacy. Comparisons of changes in all secondary outcomes will be assessed in a similar fashion.

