The Generalized Anxiety Disorder-7 (GAD-7) is a seven item screening tool for anxiety that is widely used in primary care. GAD-7 is a brief, reliable and valid measure of assessing generalized anxiety disorder [38]. The GAD-7 score (the sum of 7 items scores, 0-3) can range from 0 to 21.

Stress:

The Perceived Stress Scale (PSS) is a ten-item psychological instrument for measuring the perception of stress. It is a measure of the degree to which situations in one's life are appraised as stressful. Items were designed to tap how unpredictable, uncontrollable, and overloaded respondents find their lives.

The scale, with answers rated from 0-4, also includes a number of direct queries about current levels of experienced stress [39].

Expectation Measure:

At V1, prior to the 5th intervention session, and at V3, participants will be asked which group they believe they are assigned to, acoustic stimulation linked to brainwaves, or non-specific acoustic stimulation. The sample of primary interest will be the follow up prior to the 5th session. These expectation measures will allow evaluation of the effectiveness of blinding between the two interventions.

Participant Compensation:

Participants in this research project will receive \$100 in monetary compensation for time, trouble, and inconvenience related to study visits. Participants who do not complete the entire study will receive a prorated portion of this amount (\$25 each for completion of V1, interventions, V2, and V3). There is no additional compensation available for those who choose to cross over to receive HIRREM-SOP (visits V4-V5).

Human Subjects Protection:

Consent:

Written informed consent will be obtained by the research staff from each competent subject.

Confidentiality and Privacy:

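### Does naming blood pressure as the mixed-model outcome in the abstract leave the primary ISI analysis undefined?

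*Combined protocol and SAP*

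**What the plan says.** The Methods part of the abstract makes differential change in ISI from V1 to V3 the primary outcome and the blinding check the secondary outcome, then adds: "All other measures are tertiary and exploratory". Its analysis text follows: "Linear mixed models (LMMs) will be used to contrast longitudinal changes in systolic and diastolic blood pressure between the BCC and NCC groups". The next sentence gives the primary test as mean contrasts of ISI change from V1 to V3, and the last one reads: "Comparisons of changes in all other outcomes will be assessed in a similar fashion".

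The section Sample Size and Statistical Analysis runs in parallel. Its model sentence is "we will utilize linear mixed models (LMMs) to contrast longitudinal changes in ISI scores between the BCC and NCC groups". It continues with "Mean contrasts will be used to compare the changes in ISI between groups from V1 to V3, our primary test of efficacy", which is the same primary-test sentence as in the abstract, and closes with "Comparisons of changes in all secondary outcomes will be assessed in a similar fashion".

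Blood pressure is collected as a physiological outcome. The numbered exploratory objectives name heart rate, heart rate variability and baroreflex sensitivity, but not systolic or diastolic pressure.

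**The concern.** Two current passages describe the same analysis and name different outcomes for the only model the plan specifies. By the abstract's own ranking, blood pressure does not belong in that sentence. Read literally, the abstract names no model for ISI, so the primary contrast could be taken as a plain comparison of mean change in participants seen at both V1 and V3. No passage says which text governs.

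The choice could matter because losses are expected: "Up to 24 will be enrolled, seeking 20 to complete the protocol". A plain change comparison drops anyone without V3, whereas a mixed model on all available data keeps their V1 and any V2 scores. That affects the standard error and, depending on who is lost, can move the estimate. The pilot is meant to supply an effect size for later trials, so one should be able to tell how that estimate is produced.

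The closing sentences also differ in scope: all other outcomes in the abstract, all secondary outcomes in the analysis section. The only secondary outcome is the blinding guess, for which "participants will be asked which group they believe they are assigned to". That is a categorical answer, and a contrast of mean changes does not suit it.

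**Working it through.** The plan gives no significance level, power, effect size or SD, so there is no stated figure to reproduce. The check has two parts.

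**1. The texts side by side**

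| Element | Abstract, Methods | Sample Size and Statistical Analysis |
|---|---|---|
| Primary outcome | ISI change, V1 to V3 | ISI change, V1 to V3 |
| Mixed-model outcome | systolic and diastolic blood pressure | ISI scores |
| Primary test | mean contrasts of ISI change, V1 to V3 | identical sentence |
| Other outcomes | all other outcomes, same approach | all secondary outcomes, same approach |

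The Objectives give the same primary outcome as both columns. The second row is the only difference that touches the primary analysis. The right-hand column is the fuller text, and there the contrast directly follows an ISI model. Nothing in either column says that ISI will not be modelled or that blood pressure will not be.

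**2. What the plain-comparison reading would cost**

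Inputs from the plan: 24 enrolled and 20 completing (10 per group), so 24 − 20 = 4 lost, and 4/24 = 16.7%. The Overview speaks of 20% dropout; 20 × 1.20 = 24 and 20/(1 − 0.20) = 25, so the counts are close either way. The timing of dropout is not given, so 0 to 4 of those lost would have V2.

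Assumed, because the documents give none of these: ISI SD 5; correlations V1–V2 0.5, V1–V3 0.4, V2–V3 0.7; 12 per arm, with 2 per arm lacking V3; covariance treated as known; separate arm means at each visit.

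- Plain change, 10 per arm: √[(2/10) × 2 × 25 × (1 − 0.4)] = √6.00 = 2.45.
- Unstructured mixed model, none of the lost seen at V2. V3 is regressed on V1 with slope 0.4. Variance per arm: 25 × (1 − 0.4²)/10 + (1 − 0.4)² × 25/12 = 2.10 + 0.75 = 2.85. SE = √(2 × 2.85) = 2.39.
- Unstructured mixed model, all of the lost seen at V2. Slopes of V3 on V1 and V2: (0.4 − 0.5 × 0.7)/0.75 = 0.067 and (0.7 − 0.5 × 0.4)/0.75 = 0.667. Residual variance: 25 × (1 − 0.067 × 0.4 − 0.667 × 0.7) = 12.67. Variance per arm: 12.67/10 + (25/12) × (0.933² + 0.667² − 2 × 0.933 × 0.667 × 0.5) = 1.267 + 1.444 = 2.711. SE = √(2 × 2.711) = 2.33.
- With one of the two lost per arm seen at V2, the SE is 2.36.

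The same calculation was repeated for correlation sets (V1–V2, V1–V3, V2–V3) of (0.5, 0.5, 0.5), (0.5, 0.4, 0.7), (0.3, 0.3, 0.7), (0.6, 0.6, 0.8) and (0.6, 0.5, 0.8). The mixed-model standard error is 1.7% to 5.5% smaller than the plain one. The ratio does not depend on the SD. With no losses the unstructured model and the plain comparison both give 2.45.

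A random-intercept model on complete data would report √[(2/10) × 2 × 25 × (1 − (0.5 + 0.4 + 0.7)/3)] = √4.67 = 2.16. That is not extra precision. The point estimate equals the plain difference and its true standard error is still 2.45. The lower figure arises because equal correlations between visits are wrong under these assumptions. It is a question of covariance structure, on which both passages are silent, and naming ISI in the abstract would not settle it.

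**The case for a change.** The best case for acting is that the mismatch is real, sits in current text, and costs almost nothing to correct. The plan states no order of precedence, so a reader who sees only the abstract finds no model for the primary outcome. The abstract's closing sentence does not help, because it covers outcomes other than ISI. Under Sample Size and Statistical Analysis the closing sentence, read literally, sends a categorical blinding guess to a comparison of mean changes and leaves the exploratory measures without a stated method.

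The textual part stands: the two sentences differ, and blood pressure is out of place. The consequence does not follow. An abstract summarises, and an analyst works from the section headed for the analysis, which is explicit about ISI. The wording on secondary outcomes is a loose label. The abstract's version covers all other outcomes, and the Expectation Measure section makes clear that the guess is a choice between two groups, which no statistician would analyse as a mean change. Using all available ISI scores is what a likelihood-based mixed model does by default, so writing it down would not alter the analysis.

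**Conclusion.** The discrepancy is genuine but clerical. The plan as a whole ties the V1-to-V3 ISI contrast to an ISI mixed model, and its primary outcome, time points and primary test agree throughout. Correcting the abstract would be reasonable tidying if the document were being revised anyway, but it would alter no analysis, data collection or conclusion.

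The possible size is small: a standard error about 2% to 6% lower with the mixed model when 4 of 24 lack V3. That range depends on assumed correlations and on a plain-comparison reading that neither passage states, in a pilot that makes no formal sample size claim. If dropout is related to outcome, the two approaches could also give different estimates. The documents offer nothing from which to size that, and the analysis section already points to the mixed model.

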**Importance:**

This study will explore the use of HIRREM-SOP for insomnia, in a randomized, controlled pilot clinical trial. Results will provide important insights regarding the effect of a new generation of this novel closed-loop, acoustic stimulation, applied using a standardized protocol and a fixed number of sessions. This, in a population shown to benefit from use of the legacy technology. It will confirm feasibility of use for the upgraded technology in this population, provide estimates of effect size, and assess effectiveness of blinding for a modified placebo control condition. All will be useful for planning future controlled trials. Although not anticipated with this small pilot trial, a positive result would suggest that HIRREM-SOP might have benefit as a noninvasive, non-drug alternative for initial management of sleep trouble. The study may also help to identify characteristics of subgroups that may experience differential effects/benefits from HIRREM-SOP.

## Background:

Insomnia is the most prevalent sleep disorder and is associated with significant psychosocial and somatic pathology. Up to 50% of the US adult population reports symptoms of insomnia on a weekly basis and approximately 12% meets criteria for insomnia disorder [1]. Cross-sectional studies demonstrate that 40 to 60 percent of individuals with insomnia exhibit depressive symptoms [2, 3], 10 to 25 percent may have clinical depression, and 20 to 30 percent have an anxiety disorder [4, 5]. Chronic insomnia is associated with reduced quality of life, higher absenteeism, impaired job performance, and higher healthcare utilization [6, 7]. In a large population-based study, a linear relationship was demonstrated between insomnia prevalence and number of self-reported co-morbid medical disorders [8]. Insomnia severity has been correlated with suicidal thinking in a clinical trial population [9].

Although these cross-sectional associations are often interpreted to suggest that a variety of pathologies can result in secondary insomnia, prospective studies have found insomnia to be a risk factor for acute myocardial infarction [10] and depression [11]. In long-term follow-up of 1,741 individuals who had undergone polysomnography, insomnia was found to confer an independent and significantly increased risk for mortality [12]. More recently, chronic sleep disturbance has been suggested as a possible risk factor for Alzheimer's Disease [13].

Disturbed synchronization of neural oscillations and suboptimal proportionation, or hyperarousal of electroencephalographic (EEG) signatures, are reported in insomnia [14-16]. Autonomic dysregulation, identified by measures of heart rate variability (HRV), is reported with insomnia [17, 18]. Allostasis views the brain as the organ of central command to facilitate flexible orchestration of system functions to meet changing conditions and demands, and views disease as rigidification, or loss of dynamic range of response [19]. Closed-loop therapies with real time monitoring for modulation of biological function offer a precision-guided, patient-centric strategy for brain-based therapies [20].

High-resolution, relational, resonance-based, electroencephalic mirroring (HIRREM®) was developed by Brain State Technologies, Scottsdale, AZ. It is a commercially available, noninvasive, electroencephalic-based method to facilitate client-unique relaxation and auto-calibration of cortical neural oscillations by reflecting auditory tones in near real time [21]. HIRREM uses scalp sensors to observe brain frequencies and amplitudes in real time, and software-guided algorithmic analysis to identify and translate selected brain frequencies into audible tones of varying pitch and timing to support real-time self-optimization of brain activity. The audible tones are reflected back to the recipient bilaterally, simultaneously, in 4-8 milliseconds, providing an opportunity for the recipient to, figuratively speaking, listen to the song the brain is playing at that moment. This rapid updating regarding its pattern allows the brain a chance to auto-calibrate, self-adjust, "relax," and reset/get unstuck from what has been stuck stress/trauma response patterns. The brain electrical patterns are typically observed to shift independently, with no conscious, cognitive activity required, no operant conditioning, and no learner in the loop, towards improved balance and reduced hyperarousal. As later described, HIRREM-SOP uses the same core technology and approach.

The mechanism of this effect remains to be fully understood, but may involve resonance between reflected tones and oscillating brain networks, much like a musical instrument tuning itself. Functionally, it may be that this acoustic stimulation facilitates kindling of sleep in neuronal units, which had previously been stuck in the “on” position due to stress responses [22]. Better sleep is foundational for overall health and healing. A key aspect of observed beneficial effects may also be related to the observed improvement in downstream autonomic function, as evidenced by increased heart rate variability and baroreflex sensitivity, apparently associated with increased dynamic range and flexibility of autonomic responses managed by the brain.

Relevant Pilot Data:

Since 2011, the HIRREM Research Program at WFSM has enrolled almost 500 participants in six IRB-approved clinical studies to evaluate the effects and potential benefits of HIRREM. Use of HIRREM has been associated with reduced sleep symptomatology and reduced high frequency amplitudes in adults with insomnia [23], reduced menopausal symptoms in women [24], improved sleep in athletes with persisting post-concussion symptoms [25], reduced symptoms, and temporal lobe high frequency asymmetry in self-reported post-traumatic stress [26], and reduced symptoms of military-related traumatic stress [26]. Improved autonomic cardiovascular regulation has also been observed in those receiving HIRREM, including a cohort of adolescents with Postural Orthostatic Tachycardia Syndrome [27]. In addition, correlation has been reported between high frequency electrical brain pattern asymmetry scores at baseline, and measures of autonomic cardiovascular regulation [28].

In addition, a placebo controlled efficacy trial of in-office HIRREM for moderate to severe insomnia demonstrated a clinically meaningful reduction of insomnia symptoms ( $\geq 7$  point reduction on the ISI), and statistically significant additional benefit associated with use of HIRREM, as compared to a sham placebo of random audible tones not linked to brainwaves [29]. HIRREM was well tolerated, and the benefit was durable through the final follow up visit, 4 months after completion of the intervention (Figure 1).

Continuous recording (10 minutes) of blood pressure and heart rate also allowed for analysis of autonomic cardiovascular regulation, including multiple measures of heart rate variability and baroreflex sensitivity. Data were obtained at all study visits. Analysis demonstrated significant improvement in multiple objective measures of autonomic cardiovascular regulation including increased baroreflex sensitivity (HF $\alpha$ , and Sequence ALL) and heart rate variability (SDNN, and rMSSD), associated with this short term use of in-office HIRREM, compared to a placebo intervention of random audible tones not linked to brainwaves (Figure 2). The benefit was seen at all follow up data collections, and was durable through the final follow up at 4 months post-intervention [30]. There was no significant improvement seen in the placebo group at any time point. It is not clear whether these results reflect a cause, an effect, or both relative to the observed improvement of insomnia symptoms.

Figure 1:

[figure not shown]
[figure not shown]

Figure 2:

